8.2. Secondary Efficacy Analyses

Secondary efficacy analyses will be performed in the mITT as the primary population. All the analyses will be repeated in the PP analysis populations as corroborative and sensitivity analyses.

The analysis of Secondary Objective 1, time to BV recurrence will take into account the observed follow-up time for each participant (time-to-event analysis). For this analysis, the outcome will be the time to RBV diagnosis in days from the enrollment visit (day 1). For the participants whose RBV was diagnosed at a scheduled or unscheduled visit, their time of BV recurrence will be defined as the midpoint between the earliest time point of a positive BV diagnosis (post-baseline) and the previous observed time-point. For participants without BV recurrence at or before V4, the BV recurrence endpoint will be coded as censored, with time to recurrence defined as the elapsed time from the first dose of IP, to the earliest of: V4 time-point, the last observed time-point prior to loss to follow-up, or the time-point at which the participant became ineligible for the particular analysis population. Participants with missing time to BV recurrence will be further excluded from analyses in mITT and PP populations, including subjects who had BV recurrence diagnosed off study or subjects who were unknown whether they used any study products. The individual time to BV recurrence defined for secondary objective 1 for mITT and PP populations are also provided in [Listing 7](#).

The null hypothesis for the comparison is that there is no difference in the time to BV recurrence throughout the study between treatment arms, with a two-sided alternative that considers the possibility of a difference in either direction. Kaplan-Meier (KM) curves and associated 95% confidence bands (by treatment groups) will be presented to visually assess the treatment group-specific time-to-recurrence pattern over time. The median time to BV recurrence cannot be calculated because the assumed BV recurrence in the two treatment groups are 20% and 40%. Appropriate quartiles of the time to recurrence will be presented by each treatment group and overall. The KM curves will be presented in [Figure 3](#) for mITT population and in [Figure 4](#) for PP population. The estimate of survival time at which 25% of the subjects have recurrent BV, i.e., 25th percentile of the time to recurrence, by each treatment group and overall will be described in the footnote of the figures.

The pseudocode to fit the above analyses is below:

```
proc lifetest method=KM plots=survival(cb=hw test=atrisk) data=dataset outs=surv;
  strata treatment / test=logrank;
  Time time*censor(censored_value);
run;
```

For the Secondary Objective 2, the proportion of participants experiencing vaginal symptoms will be estimated overall, by symptom category, and by treatment group at each visit. See [Table 15](#) for mITT population and [Table 16](#) for PP population. A subject listing of BV symptoms will be presented ([Listing 8](#))

For the Secondary Objective 3, responses to the satisfaction questionnaire will be summarized overall and by treatment group. See [Table 17](#) for mITT population and [Table 18](#) for PP population. Individual subject listings will be presented for all responses to satisfaction questionnaire ([Listing 9](#)).

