**Duration of Individual Participant Participation:**

Participation will include a Screening Visit, an Enrollment Visit, and 3 clinical follow-up visits. Total participation for each participant will be approximately 100 days

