In addition, the rate of recurrence, which considers the amount of observed follow-up time for each participant, will be estimated within each treatment group along with Exact Poisson 95% confidence intervals [8]. We will use a person-time approach as follows. For participants who experience BV recurrence by any visit, the time (in days) of BV recurrence will be defined as the midpoint between the earliest time point of a positive BV diagnosis (post-baseline) and the previous observed time-point. For participants with BV recurrence diagnosed off study, the time (in days) of BV recurrence will be defined as the midpoint between the early termination time point of a positive BV diagnosis off study (post-baseline) and the previous observed time-point. For the participants who did not experience BV recurrence by V4 will contribute the total duration they participated in the study (in days). The participants who withdrew or dropped out early will contribute the number of days they participated in the study. The rate of recurrence = number of recurrence / time each person was observed, totaled for all persons. We will present the estimated recurrence rate in each group and overall, in the mITT population, then repeated in the PP population. See [Table 9](#) and [Table 10](#). The individual time to BV recurrence defined for rate of recurrence is provided in [Listing 7](#).

For efficacy response data, a subject listing of individual Amsel criteria will be provided in [Listing 6](#) for all enrolled subjects, where individual Nugent score will also be included. A summary of Amsel criteria is provided for subjects by visit and treatment group for mITT analysis population in [Table 11](#) and will be repeated in the PP analysis population as a corroborative analysis ([Table 12](#)).

As an exploratory analysis, the primary efficacy outcome measure summaries in the mITT population will be tabulated by clinical site ([Table 13](#)).

As an ancillary analysis, a summary of Nugent score by visit, category (0-3 normal; 4-6 intermediate; and 7-10 BV) and treatment group for subjects in the mITT population will be presented ([Table 14](#)).

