Listing 14: Follow-up Gynecologic and Sexual History - All Enrolled Subjects

Treatment Group	Subject ID	Visit	Study Day	Douched or Applied Any Intravaginal Products or Medications Since Last Visit	Had Sex Since Last Visit	Type of Sex (Sex in the Past 24 Hours before Visit)	How often did the subject use a condom for Vaginal Sex?
TOL-463 Vaginal Insert /Placebo	xxxxxx	xx	xx	Yes/No	Yes/No	Vaginal sex (Yes/No), Receptive oral sex (Yes/No), Anal/rectal sex (Yes/No),/ N/A	Never/Less than 50% of the time/About 50% of the time/ More than 50% of the time/Always/ N/A
TOL-463 Vaginal Insert /Placebo	xxxxxx	xx	xx	Yes/No	Yes/No	Vaginal sex (Yes/No), Receptive oral sex (Yes/No), Anal/rectal sex (Yes/No),/ N/A	Never/Less than 50% of the time/About 50% of the time/ More than 50% of the time/Always/ N/A

Listing 15: Compliance Data

Implementation Notes:

Continue for all subjects.

If all subjects received the correct treatment, only display a single “Treatment Group” column.

Include data at unscheduled visits.

Study Days of Inserts Administration column: concatenate study days by a comma.

Sort by planned treatment group, USUBJID where all subjects who completed the study listed before all subject who terminated the study, Visit number.

Planned Treatment Group	Actual Treatment Group	Subject ID	Study Day of Completion /Early Termination	Visit	Number of Inserts Used/Unused	Study Days of Insert Administration	Compliant Since Last Visit ^a (Assessment Day)	Compliance Determination Throughout the Study ^b
TOL-463 Vaginal Insert/Placebo	TOL-463 Vaginal Insert/Placebo	xxxxxx	x / N/A or N/A / x	02	x/x	x, x, x, x, x, x, x, x	Yes/No (x)	Yes/No
				03	x/x	x, U, x, x, x, x, x, x	Yes/No (x)	
				04	x/x	x, x, x, x, x, x	Yes/No (x)	

Notes: For early terminated participants, compliance with study treatment will be determined through study participation.

When a study day of insert administration is unknown, it is denoted by “U”.

^a The participant did not miss ≥ 2 consecutive or ≥ 3 nonconsecutive doses of IP since the last assessment, as recorded in data collection form.

^b For cases that could not be programmatically determined, the determination of treatment compliance throughout the study was provided by a blinded case review committee.

Listing 16: Pregnancy Reports**Pregnancy Reports – Maternal Information**

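### Time to BV recurrence has two time origins, Day 1 for recurrences and first dose for censored women, so a missing first-dose date can drop only women without an on-study recurrence

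*SAP*

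**What the plan says.** SAP 8.2, on Secondary Objective 1, defines the outcome first: "the outcome will be the time to RBV diagnosis in days from the enrollment visit (day 1"). A recurrence found at a scheduled or unscheduled visit is placed at "the midpoint between the earliest time point of a positive BV diagnosis (post-baseline) and the previous observed time-point". For a woman without recurrence by V4, the endpoint is "coded as censored, with time to recurrence defined as the elapsed time from the first dose of IP", ending at V4, at her last observation, or when she became ineligible for the population.

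The section then states: "Participants with missing time to BV recurrence will be further excluded from analyses in mITT and PP populations". It names two such groups: recurrences diagnosed off study, and women for whom it is unknown whether they used any product.

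SAP 4.5.1, note b of Listing 7 (to which Definition 3 refers back) and Protocol 10.5.4.2 also start the censored clock at first dose. None of the three gives an origin for recurrences.

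The first dose is self-administered. SAP 6.3 accepts the memory aid or returned packaging as evidence of dosing, and its mITT definition does not require a dose. Listing 15 has a code (U) for use "When a study day of insert administration is unknown". Neither document has a rule for an unknown first-dose date.

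For the recurrence rate in SAP 8.1, women without recurrence "will contribute the total duration they participated in the study (in days"). The Protocol Summary counts the screening visit within participation: "Total participation for each participant will be approximately 100 days".

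**The concern.** A Kaplan-Meier estimate and a log-rank test need one origin for everyone at risk. Here the origin depends on how the woman's follow-up ended. The first question is whether shifting the censored times by a few days reorders events and censorings. The second is who can have a missing time. A recurrence is dated from two visits. A censored time has to start from a dosing date, which may be unknown, or may not exist for a randomised woman who never dosed. With missing times excluded, inclusion in the mITT curve would then depend on outcome. At stake are the level of the secondary recurrence curves and the match between the curve and the mITT population.

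**Working it through.** **1. The plan's own figures.** SAP section 5 assumes 40% recurrence on placebo, 20% on TOL-463, 200 evaluable women, 1:1, and claims at least 85% power. With 100 per arm and a two-sided 5% test, the normal approximation gives 87.6% and exact enumeration of the uncorrected Pearson test gives 88.0%, so the claim is reproduced. The plan states no figure for time to recurrence. I use 40% and 20% as recurrence at the end of follow-up.

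**2. The clock shift alone.** In days elapsed since Day 1, the visit windows (Days 29–35, 57–63, 85–91) are 28–34, 56–62 and 84–90. Recurrence midpoints, with all visits attended in window, are:

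- found at V2: 14 to 17
- found at V3: (28+56)/2 = 42 to (34+62)/2 = 48
- found at V4: (56+84)/2 = 70 to (62+90)/2 = 76

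If the first dose is 7 days after Day 1, censoring at V2, V3 and V4 moves to 21–27, 49–55 and 77–83. None of these crosses a recurrence time, so the estimate cannot change. At 10 days, V4 censoring becomes 74–80 and overlaps 70–76.

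A simulation agrees. It used 200,000 women per scenario, visits uniform in their windows, recurrences split equally over V2–V4, and dropout of 0% or 20%; the split and the dropout pattern are assumptions. Delays of 1, 3 or 7 days change nothing to four decimals. Without dropout, a 10-day delay moves 0.4012 to 0.4076 and 0.2015 to 0.2048. A 14-day delay for every censored woman gives 0.5347 and 0.2819, which is an extreme case.

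**3. Unknown product use, the case the SAP names.** Table 3, note a, ties this to termination before V2 without a dispensing assessment. These women were normally last seen at V1, so on the Day 1 clock they are censored near time 0, before the first scheduled-visit recurrence time of 14 days. In the 20% dropout scenario, removing them (about 6.6% of women) leaves the estimates at 0.399 and 0.200.

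**4. Follow-up present, first-dose date unknown or absent.** Only women without an on-study recurrence lose their time. Without dropout, if a share f of them is removed, p becomes p/(p+(1−p)(1−f)).

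| f (assumed) | p = 0.40 | p = 0.20 |
|---|---|---|
| 5% | 0.40/(0.40+0.60×0.95) = 0.412 | 0.20/(0.20+0.80×0.95) = 0.208 |
| 10% | 0.40/(0.40+0.60×0.90) = 0.426 | 0.20/(0.20+0.80×0.90) = 0.217 |

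With 20% dropout the simulation gives 0.412 and 0.425 (placebo), and 0.209 and 0.218 (TOL-463). With the same f in both arms, the 20-point difference becomes 20.4 points (0.4124−0.2083) or 20.8 points (0.4255−0.2174).

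**5. Off-study recurrences, excluded by the same sentence.** If a share f of recurrences is removed, p becomes p(1−f)/(1−pf). At an assumed 5% and 10%, 0.40 falls to 0.38/0.98 = 0.388 and 0.36/0.96 = 0.375, and 0.20 falls to 0.19/0.99 = 0.192 and 0.18/0.98 = 0.184.

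**The case against.** The strongest reply is that the SAP never says an unknown first-dose date makes a time missing. It names two excluded groups. One consists entirely of recurrences. The other has almost no follow-up and does not move the curve. The U code in Listing 15 covers any administration day; the mock-up shows it in the Visit 3 row, not at the first dose. The inconsistency that is certain has no visible effect for short delays. The SAP also reports curves, bands, a log-rank test and the 25th percentile, not the final proportion used above, and the effect on those outputs has not been calculated.

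Most of this stands, and it limits the size of the point. It does not remove the gap. The two groups are introduced as examples of missing time, not as a complete list. Women with unknown use have a known last visit, so without a recurrence their time can be missing only because the clock starts at a dose. The SAP thus already treats an undefined first dose as a missing time. A never-dosed woman can be in the mITT population, and her censored time is undefined as written.

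Two stronger readings are tempting. A reader might infer that the rule removes only women who stayed BV-free and so raises estimated recurrence. The documents do not support that: censored women include dropouts of unknown later status, off-study recurrences are removed too, and no share is given for either group. A reader might also infer from the participation wording that screening days enter the person-time in SAP 8.1. That section bases the rate on observed follow-up time, so this is an ambiguity of wording and not a demonstrated error.

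**Conclusion.** The point holds as an inconsistency with an unguarded consequence. One analysis has two time origins and no rule for an undefined first dose; read literally, only women without an on-study recurrence can be lost for that reason. Under an assumed loss of 5–10% of such women with follow-up, the curve's endpoint rises by 1.2–2.6 points on placebo and 0.8–1.7 points on TOL-463. The actual share is unknown. Off-study exclusions work the other way, so the net direction is not established. A material bias between arms would mainly need unequal shares, and nothing in the documents indicates this. The clock shift itself is negligible for delays up to 7 days with visits attended in window. The primary proportion does not use these times and is unaffected. This is a modest defect in a secondary analysis, worth correcting because the correction is simple and keeps these women in the mITT curve.

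**What to change.** - In SAP 8.2, SAP 4.5.1 and Listing 7 (Definitions 2 and 3), measure both event and censoring times from Day 1 (randomisation), and delete the first-dose origin.
- In SAP 8.2 and Listing 7, remove unknown product use as a reason for exclusion, and state that an unknown or absent first-dose date is not one either.
- Protocol 10.5.4.2 uses first dose for censored women, and SAP section 15 now reports no departure from the protocol. Record the change of origin there.
- As a clarification only, state in SAP 8.1 and note a of Listing 7 that person-time runs from Day 1.

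The cost is SAP wording and one derivation. No new data are needed, because Day 1 is known for every randomised woman. The exclusion of off-study recurrences is a separate choice that this change leaves as it is.

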#### **10.5.4.2 Secondary Efficacy Analyses**

The secondary efficacy analyses are briefly described below. Secondary efficacy analyses will be performed in the mITT and PP analysis populations, where appropriate. Details of these analyses and any sensitivity analyses will be specified in the separate SAP document.

For the analysis of Secondary Objective 1, the median time to BV recurrence will be estimated by treatment group using Kaplan-Meier estimates. For participants who experience BV recurrence by V4, the time of BV recurrence will be defined as the midpoint between the earliest time point of a positive BV diagnosis (post-baseline) and the previous observed time-point. For participants without BV recurrence at or before V4, the BV recurrence endpoint will be coded as censored, with time to recurrence defined as the elapsed time from the first dose of IP, to the earliest of: V4 time-point, the last observed time-point prior to loss to follow-up, or the time-point at which the participant became ineligible for the particular analysis population.

For the analysis of Secondary Objective 2, the proportion of participants experiencing vaginal symptoms as assessed by the participant via the daily memory aid will be estimated overall, by symptom category, and by treatment group.

For the analysis of Secondary Objective 3, responses to the satisfaction questionnaire will be summarized overall and by treatment group. Categorical responses will be summarized using contingency tables and/or odds ratios, while continuous responses will be summarized using measures of central tendency such as the mean or median, and measures of dispersion such as the standard deviation or interquartile range.

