4.5.1. Efficacy variables

The primary efficacy analysis estimates the clinical efficacy rate of TOL-463. At each follow-up visit, the Amsel criteria will be assessed, see definition in section [3.3](#) .

For the primary analysis, a participant is deemed to experience a recurrence of BV at a follow-up visit if >2 of the Amsel criteria are met or diagnosed of BV recurrence off site. A participant has clinical suppression of BV if she meets ≤ 2 of the criteria at each observed follow-up visit through V4. See below and section [6.5](#) for handling missing BV status by TOC (visit 4).

The proportion of participants with recurrence of BV (treatment failure) up to and including V4 will be summarized overall and by treatment group along with two-sided 95% Wilson CIs. The primary analysis will be performed in the mITT analysis population. Secondary analyses of the primary outcome measure will be performed in the PP analysis population.

For the mITT analysis population, the BV status of subjects whose status cannot be determined by the TOC visit for any reason or those who withdrew or those who dropped out early will be considered ‘treatment failure’ for primary recurrence endpoint. For the PP analysis population, subjects whose BV status cannot be determined by the TOC visit for any reason will be excluded from the analysis. For secondary endpoints, missing values will be further excluded from the mITT and PP populations.

In addition, the rate of recurrence, which considers the amount of observed follow-up time for each participant, will be estimated within each treatment group along with corresponding 95% CIs. We will use a person-time approach as discussed in section 8.1.

Secondary efficacy analyses will be performed in the mITT and PP analysis populations.

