For the analysis of Secondary Objective 1, the time to BV recurrence will be estimated by treatment group using Kaplan-Meier estimates. For participants who experience clinically diagnosed BV recurrence in study by V4, the time of BV recurrence will be defined as the midpoint between the earliest time point of a positive BV diagnosis (post-baseline) and the previous observed time-point. Subjects with BV recurrence diagnosed off study will be treated as missing time to BV recurrence and excluded from the analyses for secondary endpoints, as defined above and in Section 6.5. For participants without BV recurrence at or before V4, the BV recurrence endpoint will be coded as censored, with time to recurrence defined as the elapsed time from the first dose of IP, to the earliest of: V4 time-point, the last observed time-point prior to loss to follow-up, or the time-point at which the participant became ineligible for the particular analysis population.

For the analysis of Secondary Objective 2, the proportion of participants experiencing BV symptoms will be estimated overall, by symptom category, and by treatment group.

For the analysis of Secondary Objective 3, responses to the satisfaction questionnaire will be summarized overall and by treatment group. Categorical responses will be summarized using contingency tables.

Descriptions of the analyses to assess the exploratory objective as well as other analyses that will support the primary and secondary efficacy analyses will be provided in Section 8.4.

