14. TECHNICAL DETAILS

SAS version 9.4 or above will be used to generate all TFL.

**15. SUMMARY OF CHANGES IN THE CONDUCT OF THE STUDY OR
PLANNED ANALYSES**

The analyses described in this SAP coincide with the analysis descriptions provided in the study protocol.

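### The time-to-recurrence analysis drops women known to have recurred off study, and its 25th percentile is unlikely to be reached on TOL-463

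*SAP*

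**What the plan says.** **Primary endpoint.** SAP 4.5.1 counts a woman as recurrent if she meets more than two Amsel criteria at a follow-up visit "or diagnosed of BV recurrence off site".

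**Person-time rate.** SAP 8.1 keeps her and assigns a time: "For participants with BV recurrence diagnosed off study, the time (in days) of BV recurrence will be defined as the midpoint" of the early-termination time-point and the one observed before it. Listing 7 carries this as Definition 1.

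**Time to recurrence (Secondary Objective 1).** SAP 4.5.1 states: "Subjects with BV recurrence diagnosed off study will be treated as missing time to BV recurrence and excluded from the analyses for secondary endpoints". SAP 8.2 repeats the rule for both populations ("further excluded from analyses in mITT and PP populations, including subjects who had BV recurrence diagnosed off study"), and footnote b of Listing 7 applies it to Definitions 2 and 3.

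**Protocol.** Section 10.5.4.2 gives women who recur by V4 a midpoint time. For the rest, "For participants without BV recurrence at or before V4, the BV recurrence endpoint will be coded as censored". It has no third group that is removed. SAP 15 nevertheless reports no change: "The analyses described in this SAP coincide with the analysis descriptions provided in the study protocol".

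**Summary statistic.** The protocol plans the median by arm. SAP 8.2 withdraws it: "The median time to BV recurrence cannot be calculated because the assumed BV recurrence in the two treatment groups are 20% and 40" (per cent). In its place comes "The estimate of survival time at which 25% of the subjects have recurrent BV, i.e., 25th percentile of the time to recurrence", by arm and overall, in the figure footnotes.

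**Time origin.** SAP 8.2 counts event times from Day 1 but censored times from the first dose.

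**The concern.** The SAP treats one woman in three ways: a primary event, an event with a date in the rate, and a missing value in the Kaplan-Meier and log-rank analysis. Her time is not missing, because Listing 7 derives it one column earlier. She leaves the analysis because she recurred, whereas a woman who stops without a known recurrence stays in as censored. That is selection on the outcome. It takes her out of the risk set as well as the event count.

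The percentile is a separate weakness in the same analysis. The argument used against the median applies equally to a 25th percentile in an arm assumed to reach only 20%. The SAP plans no hazard ratio, V4 recurrence probability or between-arm difference for this endpoint. The 25th percentile is therefore its only per-arm point estimate besides the curves, and the Figure 3 footnote has no entry for 'not reached'.

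**Working it through.** **Inputs from the documents.** Recurrence is 40% on placebo and 20% on TOL-463, with 200 evaluable women at 1:1, so 100 per arm (SAP 5). The test is two-sided at 5% (Protocol 10.1).

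**Inputs not in the documents.** Two figures are missing: the share *f* of recurrences diagnosed off study, and the final sample size after early closure (SAP 5). Both are treated as ranges.

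**Planned power, as a check.** For the chi-square test at 100 per arm, the pooled proportion is 0.30:

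z = [0.20 − 1.96·√(2·0.30·0.70/100)] / √[(0.24 + 0.16)/100] = (0.2000 − 0.1270)/0.0632 = 1.154, so power is 87.6%. This agrees with the SAP's figure of at least 85%.

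**Effect of deletion.** Suppose a share *f* of recurrences is deleted from an arm with true recurrence *p*. The events fall to p(1 − f) and the denominator to 1 − pf, so the apparent recurrence is p(1 − f)/(1 − pf).

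| f, both arms | Placebo | TOL-463 | Difference |
|---|---|---|---|
| 0 | 40.0% | 20.0% | 20.0 points |
| 5% | 0.380/0.980 = 38.8% | 0.190/0.990 = 19.2% | 19.6 |
| 10% | 0.360/0.960 = 37.5% | 0.180/0.980 = 18.4% | 19.1 |
| 20% | 0.320/0.920 = 34.8% | 0.160/0.960 = 16.7% | 18.1 |

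With unequal shares the contrast can move either way. Placebo 10% and TOL-463 5% gives 18.3 points; placebo 5% and TOL-463 10% gives 20.4 points.

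**Effect on the log-rank test.** As a benchmark, the hazard ratio is ln 0.8/ln 0.6 = 0.437. With 20 + 40 = 60 events, the Schoenfeld formula gives about 89% power. A simulation used 1,500 trials, constant hazard to Day 85, visits at Days 29, 57 and 85, an off-study termination day uniform between onset and the next visit, and no other dropout. Its error is about 1 point.

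| Per arm | f | Kept as events | Deleted | Censored at last negative visit |
|---|---|---|---|---|
| 100 | 5% | 87.7% | 86.1% | not run |
| 100 | 20% | 88.2% | 82.0% | 80.5% |
| 40 (assumed) | 20% | 52.3% | 45.6% | not run |

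At 100 per arm and f = 20%, estimated recurrence was 39.9% versus 20.0% when kept, 34.8% versus 16.7% when deleted, and 34.0% versus 16.5% when censored.

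**The percentile.** Ignoring dropout, the 25th percentile is reached if at least a quarter of the arm recurs. With X ~ Binomial(n, 0.20), the range below runs from P(X > 0.25n) to P(X ≥ 0.25n). Where one figure is shown, 0.25n is not a whole number and the two agree.

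| n on TOL-463 | Chance of reaching 25% |
|---|---|
| 30 | 23.9% |
| 40 | 16.1% to 26.8% |
| 50 | 18.6% |
| 60 | 13.1% to 20.7% |
| 80 | 10.7% to 16.3% |
| 100 | 8.7% to 13.1% |
| 125 | 7.6% |

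At n = 100 the chance rises to 45%–54% if true recurrence is 25%, and to 84%–89% if it is 30%. Deletion lowers it: a Kaplan-Meier simulation at 100 per arm and 20% recurrence gives about 13% with no deletion and 5% to 6% with 10% of recurrences deleted.

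For comparison, the placebo median at 40% and n = 100 would be reached with probability 2.7%, so dropping the median was reasonable. Placebo reaches its 25th percentile with probability above 99%.

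**The case against.** The best defence is that an off-study diagnosis lacks Amsel confirmation, that its date is a proxy, and that the objective is recurrence by clinical criteria. On that view, limiting events to in-study diagnoses is legitimate, and the SAP discloses the rule. The primary and secondary event sets already differ, because the mITT rule also makes undetermined status a failure. The protocol does not mention off-study diagnoses, so saying it would censor these women is an inference.

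Part of this stands. Confirmation and dating are real limits, and they justify a sensitivity analysis. They do not justify deletion. If the diagnosis does not qualify as an event, the woman has no recorded recurrence and belongs in the risk set until her last observed time-point. If it does qualify, she is an event. The SAP already accepts the diagnosis for the primary endpoint and the proxy date for the rate.

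The effect may also be small. At a 5% share the difference moves 0.4 points and power under 2 points. Symptomatic women are asked to return for an unscheduled visit, which should limit off-study diagnoses. Censoring does no better than deletion numerically (80.5% versus 82.0% power at a 20% share). These points stand, and the last is why censoring is not proposed as the main analysis.

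On the percentile, 'not reached' with a lower limit is still informative. The placebo value and the overall value (assumed 30%) should be estimable. The log-rank test, curves with bands, numbers at risk, person-time rates and primary risk difference all remain. The percentile point therefore concerns reporting, not the validity of the comparison.

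The time-origin mismatch is minor because product is dispensed at V1. The protocol itself counts censored time from first dose, so a Day 1 origin would be a change to record.

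**Conclusion.** The concern holds. The SAP contradicts itself on whether an off-study recurrence has a time, and it resolves this by an outcome-dependent exclusion that the protocol does not contain and SAP 15 does not disclose. Recurrence for Secondary Objective 1 is understated in any arm with an off-study case. The treatment contrast can shift either way if the share differs by arm.

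The textual contradiction is certain, but the size is not. With equal shares of 5% to 20%, which are assumptions, the difference falls from 20.0 to between 19.6 and 18.1 points. Log-rank power at 100 per arm falls by roughly 2 to 6 points. Under the SAP's own 20% assumption, the TOL-463 percentile is reached with probability 9% to 13% at the planned size. For an assumed 30 to 80 women it is 11% to 24%, or up to 27% if exactly 25% counts as reached. The primary analysis and sample size are not affected.

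**What to change.** - **Events.** In SAP 4.5.1, 6.5, 8.2 and Listing 7 Definitions 2 and 3, include off-study recurrences as events at the Definition 1 midpoint. Use one term throughout, since the SAP says both off site and off study.
- **Sensitivity analysis.** Censor these women at their last negative visit. Report the number of off-study recurrences by arm.
- **Origin.** Use Day 1 for events and censored times alike. SAP 8.2 also excludes women whose product use is unknown; state whether that exclusion remains once first dose is no longer the origin.
- **Summary.** Report Kaplan-Meier recurrence by arm at V2, V3 and V4 with 95% confidence intervals, and the V4 difference with its interval. The 25th percentile may stay alongside, with a 'not reached' entry and lower limit added to the Figure 3 and Figure 4 footnotes.
- **Disclosure.** In SAP 15, record each remaining departure from Protocol 10.5.4.2, including the dropped median and any change of origin.

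The cost is SAP wording and light programming. Listing 7 already derives the Definition 1 time, and the planned PROC LIFETEST step already outputs the survival estimates. No new data are needed.
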